1.0 Objectives

The objective of this study is to evaluate efficacy and tolerability of the combination of ofatumumab and lenalidomide in patients with recurrent CLL.

The primary end-point will be efficacy and an overall response rate of 40% or higher will be the target for this combination. The secondary endpoint is tolerance of the combination. Excessive toxicity will consist in a rate of grade 3-4 non-hematological toxicity in more than 50% of the patients.

2.0 Background

CLL is the most common form of adult leukemia in the United States. It has been estimated that there are approximately 150,000 individuals living with CLL in the United States. The use of combination of chemoimmunotherapy as initial therapy is associated with a high response rates. Unfortunately, once disease relapse has been observed second line treatment is less effective and responses obtained tend to be shorter(1). A treatment for second line consists in the use of the monoclonal antibody (mAb) alemtuzumab. Alemtuzumab is able to induce a response in up to 30% of the patients, but is associated with significant immunosuppression. Also, it lacks activity in patients that have developed bulk lymphadenopathies (larger than 5 centimeters)(2). Combination of purine-analogue based regimens have limited activity: the combination of fludarabine, cyclophosphamide, rituximab, alemtuzumab (CFAR) is associated with an overall response rate of 65% in patients that have received prior therapy and once patients are fludarabine refractory their median survival is less than twelve months based on our published experience (3,4).

Lenalidomide is a thalidomide derivative with immunomodulatory and anti-angiogenic properties. Lenalidomide has been studied in patients with previously treated CLL as a single-agent and has shown encouraging activity with an overall response rate of 30-50% (5,6). The mechanism of action of lenalidomide in CLL is not completely known at this point: there is indication that its activity could be mediated through the stimulation of the immune system. An increased number of circulating T-cells has been observed in patients with CLL treated with this agent. Lenalidomide has also the ability to affect the interaction between the leukemic cells and the bone marrow stromal cells and T-cells (supported by pre-clinical data) and is able to suppress TNF-alpha and alter the cytokines milieu that is potentially important for CLL proliferation (7,8).

Ofatumumab is a novel anti-CD20 mAb, and has potential advantages over rituximab in the specific setting of CLL. Ofatumumab is a fully human monoclonal antibody (IgG1) produced via a transgenic mouse technology and binds specifically to a unique epitope on the human CD20 molecule expressed on B-

cells. Ofatumumab has shown clinical activity in a phase II study of patients with refractory CLL, the overall response rate was 58% in patients refractory to fludarabine and alemtuzumab and 47% in patients with bulky lympho-nodes and refractory to fludarabine (9, 10). The toxicity profile was favorable with mainly infusion-related reactions.

On human tissue sections ofatumumab demonstrated tissue reactivity that is consistent with its target antigen specificity. Following the binding of ofatumumab to tumor B-cells clustering of CD20 into lipid rafts, as seen with rituximab, was observed. Strong differences in antibody cell-surface off-rates were detected between ofatumumab and rituximab. Ofatumumab dissociated much more slowly from surface CD20 than rituximab, corresponding to a half life of 180 minutes for ofatumumab and 90 minutes for rituximab. In this respect, both efficient clustering into rafts and a lower off-rate value for ofatumumab are important characteristics for an effective activation of the complement and may explain the superiority of ofatumumab over rituximab in CDC of B-cells. Ofatumumab-CD20 was able to induce complement-mediated lysis of freshly isolated human B-CLL tumor cells, and rituximab-resistant cells lines expressing low levels of CD20 and high levels of CD55/CD59, which is known to diminish the lytic effect of complement. Ofatumumab -CD20- and rituximab-mediated Antibody Dependent Cell-mediated Cytotoxicity (ADCC) were equivalent. In an in vivo study employing a SCID mouse tumor model, HuMax-CD20-treated animals showed a dose-dependent prolongation of survival that was superior to rituximab. A pilot pharmacokinetic study in cynomolgus monkeys demonstrated that depletion of CD20 expressing B lymphocytes occurred rapidly after antibody administration. Depletion of B cells with ofatumumab lasted four times longer than depletion observed after administration of a similar dose of rituximab (11,12)

The rationale for combining lenalidomide and ofatumumab is to potentiate the clinical efficacy of these agents without increasing their toxicity. This is based on different mechanisms of action and non-overlapping toxicity profile. The toxicity of ofatumumab consists mainly in infusion reactions and lenalidomide toxicity consisting mainly of early myelosuppression, fatigue, skin rash, diarrhea, and tumor flare. There is also the possibility that the combination will ameliorate the tumor flare reaction seen with lenalidomide because of the rapid reduction in tumor burden seen with anti-CD20 mAb therapy. Because of the debulking properties of ofatumumab, lenalidomide will be started on day 9, after two doses of ofatumumab have been administered.

Current experience with the combination of lenalidomide and the anti-CD20 mAb rituximab (MDACC study 2007-0208) shows favorable activity with 7 of the first 12 patients responding and 8 non-hematological grade >3 adverse events during the 39 treatment cycles administered (data on file).

3.0 Study Design

This is a single center open label phase II study to evaluate the efficacy and safety of the combination of lenalidomide and ofatumumab in patients with CLL who have received prior treatment. Celgene Corporation will supply lenalidomide as capsules via the RevAssist® program and GlaxoSmithKline (GSK) will supply ofatumumab for this study.

4.0 Treatment Plan

The administration of ofatumumab will be four weekly IV infusions at the dose of 300mg week 1, 1,000 mg week 2, 3 and 4, then monthly during months 2-6 and once every two months during months 7-24 (even months: 8,10,12 etc.). Lenalidomide will be given at the dose of 10mg daily. Lenalidomide will be started on day 9 – the day after the second infusion of ofatumumab and will be continued daily. Treatment duration will be 24 cycles and it will be possible to continue lenalidomide beyond 24 cycles if there is a significant benefit such as an ongoing PR or CR. Response will be evaluated after three, six, twelve, eighteen and twenty-four cycles. Only enough lenalidomide for 28 days of therapy will be supplied to the patient each cycle. Each cycle consists of 28 days. Patients with baseline creatinine clearance or calculated GFR ≥ 30 ml/min but < 50 ml/min will begin treatment at Dose Level – 1 (lenalidomide 5mg daily). These patients may be escalated to lenalidomide 10mg daily on Day 29 or later at physician discretion based on tolerability. Dose reduction steps will follow in accordance with Table 4 taken from their current dose.

Drug Dispensing Requirements

Lenalidomide:

Lenalidomide (Revlimid®) will be provided to research subjects for the duration of their participation in this trial at no charge to them or their insurance providers. Lenalidomide will be provided in accordance with the RevAssist® program of Celgene Corporation. Per standard RevAssist® requirements all physicians who prescribe lenalidomide for research subjects enrolled into this trial, and all research subjects enrolled into this trial, must be registered in and must comply with all requirements of the RevAssist® program. Prescriptions must be filled within 7 days. Only enough lenalidomide for one cycle of therapy will be supplied to the patient each cycle.

Lenalidomide capsules should be swallowed whole, and should not be broken, chewed or opened.

If a dose of lenalidomide is missed, it should be taken as soon as possible on the same day. If it is missed for the entire day, it should not be made up.

Patients who take more than the prescribed dose of lenalidomide should be instructed to seek emergency medical care if needed and contact study staff immediately.

Labeling and Lenalidomide Distribution

Lenalidomide will be shipped directly to patients via a specialty, Registered Pharmacy. Bottles will contain a sufficient number of capsules for one cycle of dosing.

Unused Lenalidomide supplies

All unused lenalidomide shall be returned via procedures outlined in the RevAssist® program.

Special Handling Instructions

Females of childbearing potential should not handle or administer lenalidomide unless they are wearing gloves.

Ofatumumab

The investigational medicinal product (IMP) is a clear colorless liquid concentrate intended for intravenous infusion after dilution in sterile, pyrogen free 0.9% sodium chloride. During infusion the IMP will be filtered using a 0.2 mm in-line filter.

Ofatumumab is supplied as a 100 mg (5 mL) vial or as a 1000 mg (50 mL) vial.

Packaging and Labeling of Ofatumumab IMP

The Ofatumomab IMP will be supplied to the site/pharmacy in cartons, each containing 10 vials. Labeling will be according to local legal requirements.

Storage of Ofatumomab IMP

The IMP will be stored refrigerated (2-8°C) in a safe and secure place. The IMP will not be frozen. A temperature log with daily readings will be kept. After dilution in 0.9% sodium chloride the IMP can be kept at room temperature and will be administered to the patient within 24 hours. Exact time of dilution will be written on the infusion bag label.

The IMP will not be utilized after the expiry date printed on the label, unless extended in writing by the sponsor (MDACC) based on ongoing stability studies.

Drug supplies will be kept in an appropriate restricted area, accessible only to the investigator, pharmacist or duly designated person. Returned, unused or expired ofatumumab will be destroyed according to MDACC guidelines.

Ofatumumab Drug Accountability and Compliance Check.

The investigator will ensure that a designated person receives IMP deliveries from GlaxoSmithKline (GSK).

Ofatumumab administration:

Pre-medication before each ofatumumab infusion must be given within 30 minutes to 2 hours prior to the treatment:

Table 1 Pre-medication Requirements prior to Ofatumumab Infusions

Infusion #	Acetaminophen (po) or equivalent	Antihistamine (iv or po) diphenhydramine or equivalent	Glucocorticoid (iv) prednisolone or equivalent
1 st	1000 mg	50 mg	50 mg
2 nd	1000 mg	50 mg	50 mg
3 rd -N th	1000 mg	50 mg	0 – 50 mg ¹

1.If the 2nd infusion has been completed without the subject experiencing any grade = 3 adverse events (AEs), pre-medication with glucocorticoid may be reduced or omitted before the 3rd to Nth infusion at the discretion of the investigator.

Ofatumumab dosing recommendation for combination therapy in CLL: the first cycle of ofatumumab in combination with chemotherapy should consist of an infusion of 300 mg on Day 1 and an infusion of 1000 of Day 8 of Cycle 1. For subsequent cycles, a dose of 1000 mg should be infused on Day 1 of each cycle.

First Infusion of 300mg Ofatumumab

The first dose administered of ofatumumab should be 300 mg to minimize infusion reactions. The initial rate of the first infusion of 300mg ofatumumab (0.3mg/ml) should be 12ml/h. If no infusion reactions occur the infusion rate should be increased every 30 minutes, to a maximum of 400 ml/h, according to Table 2. If this schedule is followed, the infusion duration will be approximately 4.5 hours.

Table 2 Infusion rate at 1st Ofatumumab infusion

Time	mL/hour
0 – 30 minutes	12
31 – 60 minutes	25

61 – 90 minutes	50
91 – 120 minutes	100
121 - 150 minutes	200
151 - 180 minutes	300
181+ minutes	400

If an infusion reaction develops, the infusion should be temporarily slowed or interrupted. Upon restart, the infusion rate should be half of the infusion rate at the time the infusion was paused. If, however, the infusion rate was 12 mL/hour before the pause, the infusion should be restarted at 12 mL/hour. Hereafter, the infusion rate may be increased according to the judgment of the investigator, in the manner described in this section.

Subsequent infusion of full dose Ofatumumab

If the previous infusion has been completed without grade ≥ 3 infusion-associated AEs, the subsequent infusion of the first full dose of ofatumumab can start at a rate of 25 mL/hour and should be doubled every 30 minutes up to a maximum of 400 mL/h, according to Table 3. Duration of the infusion will be approximately 4 hours if this schedule is followed. If the previous infusion has been completed with grade ≥ 3 infusion associated AEs, the subsequent infusion should start at a rate of 12 mL/hour according to Table 2.

Table 3 Infusion rate at subsequent Ofatumumab infusion

Time	mL/hour
0 – 30 minutes	25
31 – 60 minutes	50
61 – 90 minutes	100
91 – 120 minutes	200
121+ minutes	400

During infusion the patient should be monitored closely and appropriate measurements should be performed whenever judged necessary.

Dose Reduction: DOSE REDUCTION GUIDELINES FOR OFATUMUMAB.
 No dose reduction is planned for ofatumumab, its administration will be held for grade 3 or higher hepatic toxicity and can be omitted if clinically indicated.

Dose Reduction: DOSE REDUCTION GUIDELINES FOR LENALIDOMIDE.

Table 4: LENALIDOMIDE Dose Reduction Steps

Starting Dose 10 mg daily

Dose Level – 1 5 mg daily

Dose Level – 2 5 mg daily, day 1-21 of a 28 days cycle - or 5 mg every other day for 28 days.

Dose Level – 3 5 mg every third day

Table 4: Dose Modification Guidelines for Lenalidomide

NCI CTC Toxicity Grade	Action
Sustained (>7 days) Grade 3 neutropenia, or Grade 3 neutropenia associated with fever (temperature >38.5o C) or Grade 4 neutropenia (ANC <500/mm ³ , or <25% of baseline ANC)*.	1) Hold (interrupt dose). 2) Follow CBC weekly until resolution or stabilization 3) If neutropenia has resolved to ≤grade 2, or 50% of baseline ANC, implement one dose reduction step and continue therapy***.
Thrombocytopenia Grade 4 (platelet count <25,000/mm ³) or <25% of baseline platelet count.*	1) Hold (interrupt dose). 2) Follow CBC weekly until resolution or stabilization 3) If thrombocytopenia resolves to ≤grade 2, or 50% of baseline thrombocytopenia implement one dose reduction step and continue therapy***.
Non-blistering rash Grade 3	1) If grade 3, hold (interrupt) dose. Follow weekly until resolution or stabilization. 2) If the toxicity resolves to ≤grade 1, implement one dose reduction step and continue therapy***.
Grade 4 Desquamating (blistering) rash-any Grade Erythema multiforme Grade 3	1) Discontinue lenalidomide. Discontinue lenalidomide. Discontinue lenalidomide.
Neuropathy Grade 3	1) If grade 3, hold (interrupt) dose. Follow weekly until resolution or stabilization. 2) If the toxicity resolves to <grade 2, implement one dose reduction step and continue therapy***.
Grade 4 Sinus bradycardia/other cardiac arrhythmia Grade 2	Discontinue lenalidomide. 1) Hold (interrupt dose). Follow at least weekly until resolution or stabilization. 2) If the toxicity resolves to <grade 1, implement one dose reduction step and continue therapy***.
> Grade 3	Discontinue lenalidomide.

Allergic reaction or hypersensitivity
Grade 3

1) Hold (interrupt dose). Follow at least weekly until resolution or stabilization
2) If the toxicity resolves to \leq grade 1, implement one dose reduction step and continue therapy***.

Grade 4

Discontinue lenalidomide.

Constipation
Grade 1-2

1) Initiate bowel regimen and maintain dose level

> Grade 3

If the toxicity resolves to <grade 2, implement one dose reduction step and continue therapy***.

Venous
thrombosis/embolism
>Grade 3

Hold (interrupt) dose and start anticoagulation; restart at investigator's discretion (maintain dose level).

Hepatic or other**
non-hematologic
toxicity assessed as
lenalidomide-related
> Grade 3

1) Hold (interrupt) dose. Follow at least weekly until resolution or stabilization.
2) If the toxicity resolves to <grade 2, implement one dose reduction step and continue therapy***.

Tumor flare refractory to oral pain meds

Hold dose and differentiate tumor flare from progression. Restart therapy at the investigator's discretion.

*The use of cytokine support and/or transfusions to maintain adequate blood neutrophil and platelet counts may be considered at the investigator's discretion and as clinically indicated.

**Further dose reduction will be allowed at the discretion of the investigator in case of persistent non hematological toxicity of Grade 3 or less and in case of a change in laboratory evaluation such as platelet count, absolute neutrophil count, or hemoglobin count that indicates upcoming myelosuppression or as clinically indicated.

***Once toxicity has resolved, lenalidomide dose can be increased to 10 mg/daily at the discretion of the investigator or to the dose that is clinically indicated.

Concomitant Medication:

Tumor Lysis:

Tumor lysis syndrome (TLS) has been reported in CLL patients treated with lenalidomide and ofatumumab. Precautions must be taken to prevent TLS

including proper selection of patients with regard to renal function, correction of electrolyte abnormalities, and TLS prophylaxis and monitoring.

Allopurinol at the dose of 300mg daily will be given during the first two weeks of treatment as standard tumor lysis prophylaxis, it can then be continued at the discretion of the treating physician as clinically indicated.

Subjects should be instructed to maintain adequate hydration and maintain urinary output as an additional measure to prevent TLS. To maintain fluid intake, subjects should be instructed to drink 8 to 10 eight ounce glasses of water each day for the first 14 days of Cycle 1. Hydration levels should be adjusted according to age and clinical status, and lowered if the subject's cardiovascular status indicates the possibility of volume overload. Within the first 3 cycles of therapy, additional oral hydration should be considered concurrent with any dose escalation (or re-escalation, if permitted) of lenalidomide, when lenalidomide is restarted after having been held for any reason or in concomitance with ofatumumab administration.

Based on a patient's reaction and laboratory parameters, TLS prophylaxis may be continued or restarted as needed as clinically indicated.

Prophylactic hepatitis treatment will be initiated if clinically indicated.

Anticoagulation Consideration:

Lenalidomide increases the risk of thrombotic events in patients who are at high risk or who have a history of thrombosis in particular when combined with other drugs known to cause thrombosis. When lenalidomide is combined with other agents such as steroids, (e.g. dexamethasone, prednisone, erythropoietin, Adriamycin and daunorubicin), anthracyclines (Doxil, Adriamycin), the risk of thrombosis is increased. Treating physicians may consider the use of aspirin (81mg or 325mg) or low molecular weight heparin in patients at high risk for thrombotic events.

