The first time point to evaluate efficacy and toxicity will be at completion of cycle 6 of treatment. Toxicity will be monitored closely during the entire treatment, but toxicities occurring after cycle 6 will not be applied to the stopping boundaries. The descriptive statistical analysis can be used to explore the data, including histograms or box-plots, proportions, mean, standard deviations. The Fisher's exact test will be used for the univariate analysis on categorical variables (response variable with Yes versus No, for example). The t-test or Wilcoxon test will be used for continuous variables (Age and WBC, for example). Descriptive statistical analysis will also be used to report correlative studies and the quality of life questionnaire.

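### Section 4.0 gives two conflicting ofatumumab schedules and does not say which one governs

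*Combined protocol and SAP*

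**What the plan says.** Section 4.0 describes ofatumumab dosing twice.

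- **Schedule A, opening paragraph of section 4.0.** Ofatumumab is to be given as "four weekly IV infusions at the dose of 300mg week 1, 1,000 mg week 2, 3 and 4, then monthly during months 2-6", and after that "once every two months during months 7-24 (even months: 8,10,12 etc". No dose is printed for the infusions after week 4, and no day within the month. The same paragraph defines a cycle as 28 days and states: "Treatment duration will be 24 cycles".
- **Schedule B, paragraph under the ofatumumab administration heading, between the pre-medication table and the infusion-rate tables.** It is introduced as a dosing recommendation for combination treatment of CLL and says that "the first cycle of ofatumumab in combination with chemotherapy should consist of an infusion of 300 mg on Day 1 and an infusion of 1000" (no unit printed after the last figure) on Day 8. It continues: "For subsequent cycles, a dose of 1000 mg should be infused on Day 1 of each cycle". No last cycle is given.

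Section 10.0 fixes when exposure matters most for the analysis: "The first time point to evaluate efficacy and toxicity will be at completion of cycle 6 of treatment", and "toxicities occurring after cycle 6 will not be applied to the stopping boundaries".

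**The concern.** A phase II trial tests one regimen. Here the text that staff would use to order and give the antibody describes two regimens, and no sentence in the available sections says which applies. They agree through Day 8, part at weeks 3 and 4, agree in frequency in cycles 2 to 6, and part again from cycle 7.

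The cycle 1 conflict matters most for the statistics. It falls before the cycle 6 evaluation, and inside the only period whose toxicities count towards the stopping boundaries. If some patients received one schedule and some the other, the response count judged against 3 of 19 and 10 of 36, and the toxicity count judged against the Bayesian boundaries, would each mix two exposures. Apart from the statistics, an unresolved contradiction in the dosing instructions for an investigational drug is a safety matter.

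**Working it through.** **The plan's own design figures.** Section 10.0 states a two-stage minimax design with 19 + 17 = 36 patients, stopping at 3 or fewer responses of 19 and concluding ineffective at 10 or fewer of 36. With X1 ~ Bin(19, p) and X2 ~ Bin(17, p):

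- Early termination at p = 0.20: P(X1 ≤ 3) = 0.455 (plan: 0.46).
- P(declare active) = Σ over x = 4 to 19 of P(X1 = x) · P(X2 ≥ 11 − x). This is 0.0861 at p = 0.20 (plan: at most 0.1) and 0.9024 at p = 0.40 (plan: 90%).

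The design reproduces. The problem lies in what is being tested, not in the size of the test.

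**Assumptions for the dose comparison.**

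1. One month equals one 28-day cycle.
2. Each schedule A infusion after week 4 is 1,000 mg (no dose is printed there).
3. The figure without a unit in schedule B is in mg.
4. Schedule B runs to cycle 24 (no end is printed).

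The infusion counts in cycle 1 need none of these. The cycle 1 doses need only assumption 3.

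**Schedule A.**

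- Cycle 1: 300 + 3 × 1,000 = 3,300 mg, 4 infusions.
- Through cycle 6: 3,300 + 5 × 1,000 = 8,300 mg, 4 + 5 = 9 infusions.
- Months 8, 10, …, 24 add 9 infusions: 8,300 + 9 × 1,000 = 17,300 mg, 18 infusions.

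**Schedule B.**

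- Cycle 1: 300 + 1,000 = 1,300 mg, 2 infusions.
- Through cycle 6: 1,300 + 5 × 1,000 = 6,300 mg, 7 infusions.
- Through cycle 24: 1,300 + 23 × 1,000 = 24,300 mg, 25 infusions.

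| Cumulative through | A: infusions / mg | B: infusions / mg | A − B (mg) |
|---|---|---|---|
| Day 8 | 2 / 1,300 | 2 / 1,300 | 0 |
| Cycle 1 | 4 / 3,300 | 2 / 1,300 | +2,000 |
| Cycle 3 | 6 / 5,300 | 4 / 3,300 | +2,000 |
| Cycle 6 | 9 / 8,300 | 7 / 6,300 | +2,000 |
| Cycle 8 | 10 / 9,300 | 9 / 8,300 | +1,000 |
| Cycle 10 | 11 / 10,300 | 11 / 10,300 | 0 |
| Cycle 12 | 12 / 11,300 | 13 / 12,300 | −1,000 |
| Cycle 24 | 18 / 17,300 | 25 / 24,300 | −7,000 |

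At cycle 6 the ratio is 8,300 / 6,300 = 1.32, and the whole difference comes from cycle 1. Over cycles 7 to 24 alone, A gives 9 infusions and B gives 18. If B ended after cycle 6, its total would be 7 infusions / 6,300 mg, so B's full-course total ranges from 6,300 to 24,300 mg depending on assumption 4.

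**Can other text settle it?** Section 2.0 says that "lenalidomide will be started on day 9, after two doses of ofatumumab have been administered"; both schedules have given exactly two doses by then. The pre-medication table separates the first, second and all later infusions, which also fits both.

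**Months against cycles.** Treatment lasts 24 × 28 = 672 days, or 672 / 30.44 = 22.1 calendar months. If schedule A's months were calendar months with dosing on the first day of each, month 6 would start at about day 153 (within the 168 days of six cycles, so still 9 infusions). Month 22 would start at about day 640, and month 24 at about day 701, after treatment ends. Then 17 of the 18 infusions would fall inside the treatment period.

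**The case against.** The strongest reply is that the two texts do not have equal standing. Schedule A opens the Treatment Plan and is written as a directive. Schedule B calls itself a recommendation and refers to use with chemotherapy, whereas this trial combines ofatumumab with lenalidomide. It may be general text carried over from elsewhere.

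That is a fair reading, but the document does not state it. Schedule B's lead-in speaks of combination treatment of CLL, which describes this trial. Its verb form is the one used for the neighbouring infusion instructions that staff are plainly meant to follow. It is also the only place that prints both a dose and a day for later cycles, so a reader filling the gaps in schedule A is led straight to it.

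Some of the other objections stand:

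- The appendices were not available, so the absence of a governing statement is established only for the sections seen.
- The full-course contrast depends on an assumed end for schedule B, and even the 32% at cycle 6 uses doses not printed in schedule A.
- Section 9.0 says that ofatumumab adverse events were concentrated on the first infusion day, where the texts agree. Section 4.0 also allows infusions to be held or left out on clinical grounds, so exposure will vary anyway. No effect on response or toxicity rates has been estimated.
- Reading months as 28-day cycles is natural, which makes the calendar point minor.
- Sections 4.0 and 8.0 place a response assessment after cycle 3, before section 10.0's first evaluation; the gap at cycle 3 is the same 2,000 mg.

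None of this removes the conflict of four against two infusions in cycle 1.

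**Conclusion.** The concern holds. Section 4.0 contains two incompatible ofatumumab schedules with no stated order of precedence, so the regimen that the response test and the toxicity boundaries judge is not uniquely defined.

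The firm findings, which need no dose assumption, are four against two infusions in cycle 1 and, from cycle 7, dosing every two months against every cycle. Under assumptions 1 to 3 the difference at the cycle 6 evaluation is two infusions and 2,000 mg. The cycle 24 contrast is indicative only.

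The error rates and sample size stand, and there is no evidence in the documents that patients were treated differently. The correction is nonetheless necessary, because the contradiction sits in the dosing instructions themselves.

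**What to change.** Reconcile the two paragraphs of section 4.0 into a single ofatumumab schedule, expressed in cycles and days, with the dose and unit printed for every infusion and the last infusion stated. Remove the text that does not govern this trial, or mark it as not applicable. Which schedule applies is for those responsible for the treatment to state; this review takes no view.

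If patients have already been treated, report the number of ofatumumab infusions and the cumulative dose actually received through cycle 6 alongside the response and toxicity rates, so that a reader can see whether one regimen or a mixture was evaluated.

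The cost is one protocol clarification, with the agreement and IRB approval that section 11.0 requires for amendments. Sample size, alpha, power and the stopping boundaries do not change.

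### The 50%-of-baseline restart limb for lenalidomide has no absolute floor, so a low-baseline patient can meet the restart and hold rules at the same count

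*Combined protocol and SAP*

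**What the plan says.** All of the rules below are in Section 4.0, Dose Modification Guidelines for Lenalidomide, unless another section is named.

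- **Platelet hold.** The trigger is "Thrombocytopenia Grade 4 (platelet count <25,000/mm"³), or a count below 25% of baseline.
- **Platelet restart.** "If thrombocytopenia resolves to ≤grade 2, or 50% of baseline thrombocytopenia implement one dose reduction step and continue therapy".
- **ANC hold.** The triggers are "Sustained (>7 days) Grade 3 neutropenia, or Grade 3 neutropenia associated with fever", or "Grade 4 neutropenia (ANC <500/mm"³), or a count below 25% of baseline.
- **ANC restart.** "If neutropenia has resolved to ≤grade 2, or 50% of baseline ANC", again one dose level lower.
- **During the hold.** "Follow CBC weekly until resolution or stabilization".
- **Footnotes.** The first says "The use of cytokine support and/or transfusions to maintain adequate blood neutrophil and platelet counts may be considered", at the investigator's discretion. The second permits further reduction, and the third permits re-escalation once toxicity has resolved. None sets a minimum count for restart.
- **Entry (Section 5.0).** Inclusion criterion 4 admits patients from 30,000 platelets. No minimum ANC is listed. Exclusion criterion 6 leaves laboratory abnormalities that pose unacceptable risk to judgement.

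**The concern.** In each row the absolute hold limit is a separate trigger that applies at every baseline. The restart rule joins two limbs with *or*, so reaching half of baseline is enough by itself. When baseline is low, half of baseline can be smaller than the hold limit. The same row then tells the investigator both to hold and to resume at one count.

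Section 2.0 describes "lenalidomide toxicity consisting mainly of early myelosuppression" among other effects, so the rule governs one of the drug's main expected toxicities. Read literally, the table allows lenalidomide to resume at a platelet count that it labels grade 4, and an unchanged next count would trigger the hold again. Section 4.0 also lets physicians consider aspirin or low molecular weight heparin for patients at high thrombotic risk, which makes dosing during severe thrombocytopenia more than a formality.

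**Working it through.** The plan has no derived figure to reproduce here. The limits are stated rules, and the check is whether they are compatible.

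**Inputs.** From the dose modification table: absolute hold limits of 25,000 (platelets) and 500 (ANC), a relative hold limit of 25% of baseline, and a relative restart limit of 50% of baseline. From Section 5.0: minimum entry platelets of 30,000 and no listed ANC minimum.

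**Reading adopted.** The platelet row literally refers to half of baseline *thrombocytopenia*. I read this as half of the baseline platelet count, in line with the ANC row and with the 25% hold limb of the same row.

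**Formulas.** For baseline B, the hold applies below max(absolute limit, 0.25B), because the hold limbs are alternatives. The relative restart limit is 0.50B. The rules conflict where 0.50B is below the hold limit:

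- Platelets: 0.50B < 25,000 when B < 50,000.
- ANC: 0.50B < 500 when B < 1,000.
- Where 0.25B is the larger hold limit, 0.50B always exceeds it, so there is no conflict.

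| Count | Baseline | 25% of baseline | Hold below | Half of baseline | Restart allowed while still in hold range |
|---|---|---|---|---|---|
| Platelets | 30,000 | 7,500 | 25,000 | 15,000 | 15,000 to <25,000 |
| Platelets | 40,000 | 10,000 | 25,000 | 20,000 | 20,000 to <25,000 |
| Platelets | 45,000 | 11,250 | 25,000 | 22,500 | 22,500 to <25,000 |
| Platelets | 50,000 | 12,500 | 25,000 | 25,000 | none |
| ANC | 600 | 150 | 500 | 300 | 300 to <500 |
| ANC | 800 | 200 | 500 | 400 | 400 to <500 |
| ANC | 1,000 | 250 | 500 | 500 | none |

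**Platelet example, B = 30,000.**

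1. The count falls to 12,000, and 12,000/30,000 = 40.0%. The absolute limit triggers the hold; the 25% limit of 7,500 is not reached.
2. The count recovers to 16,000, and 16,000/30,000 = 53.3%. The restart limb is met.
3. 25,000 − 16,000 = 9,000, so the count is still 9,000 under the hold limit.

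**ANC example, B = 800.** A fall to 350 (350/800 = 43.8%) triggers the hold. Recovery to 420 (420/800 = 52.5%) meets the restart limb, 80 below the limit of 500.

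**The case against.** The best defence is that baseline-relative limits are deliberate. The protocol admits patients with low counts from their disease, and Section 9.0 treats myelosuppression as an expected part of therapy. The table does not print the grade 2 limits. If grade 2 platelets begin at 50,000 (an assumption), a patient with a baseline of 30,000 to <50,000 who merely returns to baseline could restart only through the 50% limb. How much cytopenia to accept in such patients is a clinical judgement, and the documents give no outcome data against the choice made.

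Part of this stands: the relative limb has a purpose and should stay. It does not remove the conflict, because the hold was not made relative. The absolute limits bind at every baseline, and 25% of baseline is only an extra trigger. If the hold is meant to prevail, the 50% limb has no effect below 25,000 or 500, and the table should say so. If treatment below those counts is intended, the hold needs rewording. Either intention calls for a change.

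The mitigations also stand, but none is a floor. Restart is one dose level lower, CBCs are weekly during the hold, and transfusion, cytokines and further reduction are available at discretion. Reach is narrow too. The clear case needs a low baseline, a nadir below half of it, and a recovery that stalls in a window at most 10,000 platelets wide.

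A reader might infer more than the documents support, in three ways:

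- **Grade 3 neutropenia.** It may seem that the 50% limb also conflicts with the grade 3 hold. The table does not print the grade 3 range, and grade 3 alone is not a trigger: it must be febrile or last more than 7 days. An afebrile restart in that range does not in itself meet the hold rule.
- **Counts that never fell below half of baseline.** A platelet count of 20,000 from a baseline of 30,000 (66.7%) is held, and it may seem to qualify for restart at once. The rule speaks of a count that *resolves to* the level, and the text does not settle whether this patient qualifies. I give that case no weight.
- **The toxicity stopping rule in Section 10.0.** It counts non-hematological events only, but it is a trial-level rule with no bearing on an individual restart threshold.

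**Conclusion.** The hold and restart rules contradict each other for baseline platelets of 30,000 to <50,000 and for baseline ANC below 1,000. The overlap is widest for platelets at the entry minimum (15,000 to <25,000) and closes at 50,000. For ANC it closes at 1,000.

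The conclusion depends on reading the platelet limb as half of the baseline platelet count. The thresholds themselves are printed in the table. Appendix J is not in the text available to me, but Section 9.0 cites it for reporting myelosuppression, not for dosing.

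The share of the 36 planned patients with such baselines is not given, so the number affected cannot be estimated. This is a dosing-safety inconsistency that should be corrected. A reader should not infer that it weakens the trial's efficacy conclusion: the response analysis, sample size and error rates do not depend on it.

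**What to change.** Keep the grade 2 limb in both rows and reword the other limb:

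- **Platelet row:** at least 50% of baseline platelet count AND platelets ≥25,000/mm³. This also replaces the loose reference to baseline thrombocytopenia.
- **ANC row:** at least 50% of baseline ANC AND ANC ≥500/mm³.
- **Baseline ANC below 500:** the absolute hold is already met at entry and a 500 floor would exceed the patient's own baseline. For these patients, do not apply the absolute hold, retain the hold below 25% of baseline, and restart on return to baseline ANC. At a baseline of 400, for example, the hold applies below 100 and restart is at 400. No equivalent platelet rule is needed, because entry starts at 30,000.

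The edit is limited to the wording of two rows. The clinical cost is a longer hold for some patients, including some whose low counts are due to disease:

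| Count | Baseline | Restart on 50% limb now | Restart with floor | Floor as share of baseline |
|---|---|---|---|---|
| Platelets | 30,000 | 15,000 | 25,000 | 83.3% |
| Platelets | 40,000 | 20,000 | 25,000 | 62.5% |
| ANC | 600 | 300 | 500 | 83.3% |
| ANC | 800 | 400 | 500 | 62.5% |

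Nothing changes for baseline platelets of 50,000 or more, or for baseline ANC of 1,000 or more. The floor removes the contradiction but adds no buffer: a small fall from 25,000 or 500 triggers the hold again.
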